10.4 Subject Confidentiality

Personal and sensitive data will be treated as confidential. The results of the clinical trial will be made available for review by authorized representatives of the Sponsor and/or submitted to the IRB/IEC, and regulatory authorities.

Prior to the subject's enrollment in the clinical trial, the subject's consent is required for the data to be used for these purposes and to gain direct access to their medical records for data verification purposes. The subject must be assured that their identity will be protected. To facilitate this, a unique identification number will be assigned and it will be used when reporting study-related data.

Additionally, in the US, the Health Insurance Portability and Accountability Act of 1996 ("HIPAA") requires that all subjects grant permission to use their personal health information. Therefore, in addition to the protocol-specific ICF, each subject located in the United States (US) will be asked to provide authorization to use his/her personal health information by signing a separate HIPAA Authorization Form.

10.5 Study Monitoring

It is understood that the Sponsor or its designee (e.g., the CRA) will contact and visit the PI/SI regularly for monitoring purposes. The CRA will be allowed, on request, to inspect the various records of the clinical trial (i.e., eCRFs, source documents, and any other pertinent data), provided that subject confidentiality is maintained in accordance with local requirements. It will be the CRA's responsibility to inspect the eCRFs at regular intervals throughout the clinical trial, to verify adherence to the protocol and to ensure the completeness, consistency, and accuracy of the data entered. The CRA must have access to all subject records needed to verify the entries on the eCRF. The PI/SI (or a designee) agrees to cooperate with the CRA to ensure that problems detected during these monitoring visits are resolved.

In addition, the Sponsor may perform a Clinical Quality Assurance (CQA) audit randomly at a sample of clinical sites, or for cause as warranted. The CQA audit will examine the accuracy of source documentation, record retention, data management, and compliance. These audits will be independent of routine monitoring by the CRA with prior written notification provided to the site.

10.6 Case Report Forms and Study Records

This clinical trial will utilize an electronic data capture system for the management of clinical data. The data will be collected in electronic form (i.e., via an eCRF) to allow for data entry at the site from source documentation directly into the electronic database. Access to the electronic system will be restricted, and users will only be able to access the system via authorized individual accounts. All changes to data in the database will be tracked and time

stamped automatically, including updates to data entries and resolution of data queries generated by the CRA or data reviewer.

Training will be provided to all system users based on their individual access and use requirements initially and ongoing throughout the course of the clinical trial as needed. Documentation of training will be kept in the site regulatory file and in Sponsor's TMF.

A comprehensive Data Management Plan will be written outlining the standard operating procedures, internal/external security safeguards, system and change controls, and training procedures and will be filed in the Sponsor's TMF. A cumulative record will also be kept of the user and access privileges for all authorized users across the clinical trial.

The system and procedures for electronic database set-up, entry, review, access, security, and auditing are designed in specific compliance with 21 CFR 11 and the Food and Drug Administration's (FDA's) Part 11 Guidance for Industry supplement "Computerized Systems Used in Clinical Investigations" dated May 2007. Any additional electronic systems that may be used by vendors (e.g., PK) or clinical sites (e.g., electronic medical records used as source documents) should comply with these same regulatory standards.

As a final step in the data management process, a 100% quality control review will be performed on the key efficacy and safety parameters. In addition, a random subject sample (approximately 10%) will be selected to perform a database audit. The purpose of this audit is to detect systematic and random errors.

10.7 Data Safety Monitoring Board

A Data Safety Monitoring Board (DSMB) is not planned for this study since treatment is unblinded to study personnel and the overall small size of the study generally limits the value of pooling data across the study population. All study PI/SI will have the ability to assess benefit:risk for each subject in almost real time. The study medical monitor and Sponsor will have access to safety and efficacy data from across the entire study population. The study design limits the duration of ATR-101 treatment duration and assesses safety every 2 weeks.

10.8 Protocol Deviations

Protocol deviations from inclusion/exclusion criteria, concomitant medication restrictions, and from any other protocol requirements that could, at least hypothetically, result in significant risk to the subject and/or affect the outcome of the study will be collected. Additionally, nonadherence to the study procedures or schedule as defined by the protocol such as a missed procedure or an out-of-window study visit will be documented as protocol deviations.

10.9 Access to Source Documentation

The PI/SI must permit the authorized Sponsor, agents of the Sponsor, and regulatory agency employees to enter and inspect any site where the drug or records pertaining to the drug are held and to inspect and copy all records relating to an investigation including subject records. To ensure the accuracy of data submitted, it is mandatory that representatives of the Sponsor and of the regulatory agencies have direct access to source documents (e.g., subject medical records,

charts, laboratory reports) for the purpose of quality assurance audits either by Millendo or their appointed representatives. Subject confidentiality will be protected at all times.

10.10 Data Generation and Analysis

Data processing and management will be performed by the Sponsor or its designee. Data will be promptly entered into the study database and reviewed and issues resolved prior to database closure.

Personal and sensitive personal data will be treated as confidential. The results of the study will be made available for review by authorized representatives of the Sponsor and/or submitted to the IRB/IEC, and regulatory authorities. Prior to the subject's enrollment in the study, the subject's consent is required for the data to be used for these purposes and to gain direct access to their medical records for data verification purposes. The subject must be assured that their identity will be protected. To facilitate this, a unique identification number will be assigned and it will be used when reporting study-related data.

10.11 Retention of Data

Copies of all study documents should be retained by the PI for at least 2 years after the last approval of a marketing application in an ICH region and until there are no pending or contemplated marketing applications in an ICH region or at least two years have elapsed since the formal discontinuation of clinical development of the investigational product, in accordance with 21 CFR 312.62. These documents should be retained for a longer period, however, if required by regulatory requirements or by agreement with the Sponsor. It is the responsibility of the Sponsor to inform the Investigator/institution as to when these documents no longer need to be retained. The final database will be archived by the Sponsor according to the regulatory requirements.

10.12 Financial Disclosure

PI and SI are required to provide full disclosure of any financial relationship to the Sponsor or its designee(s) prior to participation in any trial-related activities. Additionally, PI/SI are required to promptly provide updated information to the Sponsor or its designee(s) regarding any relevant changes in financial interests that occur during the course of the clinical trial and for 1 year after completion of the clinical trial. For additional guidance, refer to 21 CFR 312.53(c) (4), 312.64(d), 812.43(c) (5), 812.110(d).

10.13 Premature Termination of the Study

If the study is prematurely terminated or suspended, the Sponsor will promptly inform the PI/SI /institutions and the regulatory authority(s) of the termination or suspension and the reason(s) for the termination or suspension.

10.14 Clinical Study Report

A CSR will be written for this study with a structure and content that will conform to the ICH guidance, “Structure and Content of Clinical Study Reports, ICH Topic E3, July 1996”.

10.15 Subject Insurance and Indemnity

The Sponsor will provide insurance in accordance with local guidelines and requirements as a minimum for the subjects’ participating in this study. The terms of insurance will be kept in the Sponsor’s regulatory files.

10.16 Amendments to the Protocol

Modifications of the signed protocol are only possible by approved protocol amendments and with the agreement of all responsible persons. The procedure for approval of a protocol amendment is identical to that for approval of the protocol. The IRB/IEC must be informed of all protocol amendments and should be asked for its opinion as to whether a full re-evaluation of the ethical aspects of the study is necessary by the committee. This should be fully documented.

The PI/SI must not implement any deviation from or change to the protocol without discussion and agreement by the Sponsor in writing and prior review and documented approval/favorable opinion of the amendment from the relevant IRB or IEC, except where it is necessary to eliminate an immediate hazard to study subjects or where the change(s) involves only logistical or administrative aspects of the study (e.g., change in monitor or change of telephone number).

Protocol amendments will be submitted to the appropriate authority(s) as required by the applicable regulatory requirement(s).

Appendix 3 Drugs that Prolong the QT/QTc interval

List A. Drugs that prolong the QT Interval that are prohibited.

Generic Name	Brand Name	Class/Clinical Use	Comments
Amiodarone	Pacerone®	Anti-arrhythmic/abnormal heart rhythm	Females>Males, TdP risk regarded as low
Arsenic trioxide	Trisenox®	Anti-cancer/Leukemia	
Astemizole	Hismanal®	Antihistamine/Allergic rhinitis	No Longer available in U.S.
Azithromycin	Zithromax®	Antibiotic/bacterial infection	
Bepidil	Vascor®	Anti-anginal/heart pain	Females>Males
Chloroquine	Aralen®	Anti-malarial/malaria infection	
Chlorpromazine	Thorazine®	Anti-psychotic/Anti-emetic/schizophrenia/nausea	
Cisapride	Propulsid®	GI stimulant/heartburn	No longer available in U.S.
Citalopram	Celexa®	Anti-depressant/depression	
Clarithromycin	Biaxin®	Antibiotic/bacterial infection	
Disopyramide	Norpace®	Anti-arrhythmic/abnormal heart rhythm	Females>Males
Dofetilide	Tikosyn®	Anti-arrhythmic/abnormal heart rhythm	Females > Males
Domperidone	Motilium®	Anti-nausea/nausea	Not available in U.S.
Droperidol	Inapsine®	Sedative; Anti-nausea/ anesthesia adjunct, nausea	
Erythromycin	E.E.S.®	Antibiotic; GI stimulant/bacterial infection; increase GI motility	Females>Males
Erythromycin	Erythrocin®	Antibiotic; GI stimulant/bacterial infection; increase GI motility	Females>Males
Escitalopram	Cipralextm®	Anti-depressant/Major depression/Anxiety disorders	
Escitalopram	Lexapro®	Anti-depressant/Major depression/Anxiety disorders	
Flecainide	Tambocor®	Anti-arrhythmic/abnormal heart rhythm	
Halofantrine	Halfan®	Anti-malarial/malaria infection	Females>Males
Haloperidol	Haldol®	Anti-psychotic/schizophrenia, agitation	TdP risk with I.V. or excess dosage
Ibutilide	Corvert®	Anti-arrhythmic/abnormal heart rhythm	Females>Males
Levomethadyl	Orlaam®	Opiate agonist/pain control, narcotic dependence	Not available in U.S.
Mesoridazine	Serentil®	Anti-psychotic/schizophrenia	
Methadone	Dolophine®	Opiate agonist/pain control, narcotic dependence	Females>Males
Methadone	Methadose®	Opiate agonist/pain control, narcotic dependence	Females>Males
Moxifloxacin	Avelox®	Antibiotic/bacterial infection	
Pentamidine	NebuPent®	Anti-infective/pneumocystis pneumonia	Females>Males
Pentamidine	Pentam®	Anti-infective/pneumocystis pneumonia	Females>Males
Pimozide	Orap®	Anti-psychotic/Tourette's tics	Females>Males
Probucof	Lorelco®	Antilipemic/Hypercholesterolemia	No longer available in U.S.
Procainamide	Pronestyl®	Anti-arrhythmic/abnormal heart rhythm	
Procainamide	Procan®	Anti-arrhythmic/abnormal heart rhythm	
Quinidine	Quinaglute®	Anti-arrhythmic/abnormal heart rhythm	Females>Males
Quinidine	Cardioquin®	Anti-arrhythmic/abnormal heart rhythm	Females>Males
Sevoflurane	Ulane®	Anesthetic, general/anesthesia	Label warning for patients with congenital long QT or patients taking QT prolonging drugs
Sevoflurane	Sojourn®	Anesthetic, general/anesthesia	Label warning for patients with congenital long QT or patients taking QT prolonging drugs
Sotalol	Betapace®	Anti-arrhythmic/abnormal heart rhythm	Females>Males
Sparfloxacin	Zagam®	Antibiotic/bacterial infection	No longer available in U.S.
Terfenadine	Seldane®	Antihistamine/Allergic rhinitis	No longer available in U.S.
Thioridazine	Mellaril®	Anti-psychotic/schizophrenia	
Vandetanib	Caprelsa®	Anti-cancer/Thyroid cancer	

LIST B. Drugs with conditional risk of QT prolongation, to be used with caution

Generic Name	Brand Name	Class/Clinical Use	Comments
Amisulpride	Solian® and others	Antipsychotic, atypical	Risk of TdP with overdose - not available in US
Amitriptyline	Elavil®	Tricyclic Antidepressant /depression	Risk of TdP with overdosage
Ciprofloxacin	Cipro®	Antibiotic/bacterial infection	Drug interaction risk - metabolic inhibitor
Clomipramine	Anafranil®	Tricyclic Antidepressant /depression	
Desipramine	Pertofrane®	Tricyclic Antidepressant /depression	Risk of TdP with overdosage
Diphenhydramine	Benadryl®	Antihistamine/Allergic rhinitis, insomnia	Risk of QT increase/TdP in overdosages
Diphenhydramine	Nytol®	Antihistamine/Allergic rhinitis, insomnia	Risk of QT increase/TdP in overdosages
Doxepin	Sinequan®	Tricyclic Antidepressant /depression	
Fluconazole	Diflucan®	Anti-fungal/fungal infection	Drug interaction risk metabolic inhibitor. Can also increase QT at high doses - 800 mg/day
Fluoxetine	Sarafem®	Anti-depressant/ depression	
Fluoxetine	Prozac®	Anti-depressant/ depression	
Galantamine	Reminyl®	Cholinesterase inhibitor /Dementia, Alzheimer's	
Imipramine	Norfranil®	Tricyclic Antidepressant /depression	TdP risk with excess dosage
Itraconazole	Sporanox®	Anti-fungal/fungal infection	Drug interaction risk - metabolic inhibitor
Ketoconazole	Nizoral®	Anti-fungal/fungal infection	Prolongs QT & Drug interaction risk – metabolic inhibitor.
Nortriptyline	Pamelor®	Tricyclic Antidepressant /depression	
Paroxetine	Paxil®	Anti-depressant/ depression	
Protriptyline	Vivactil®	Tricyclic Antidepressant /depression	
Ritonavir	Norvir®	Protease inhibitor/HIV	
Sertraline	Zoloft®	Anti-depressant/ depression	
Solifenacin	VESIcare®	muscarinic receptor anatagonist/treatment of overactive bladder	
Trazodone	Desyrel®	Anti-depressant/ Depression, insomnia	
Trimethoprim-Sulfa	Septra® or Bactrim®	Antibiotic/bacterial infection	Also available in DS (double strength)
Trimipramine	Surmontil®	Tricyclic Antidepressant /depression	

LIST C. Drugs with possible risk of QT prolongation, to be used with caution

Generic Name	Brand Name	Class/Clinical Use	Comments
Alfuzosin	Uroxatral®	Alpha 1-blocker/Benign prostatic hyperplasia	
Amantadine	Symmetrel®	Dopaminergic/Anti-viral/ Anti-infective/ Parkinson's Disease	
Arteminol+piperazine	Eurartesim®	Anti-malarial	Not available in U.S.
Atazanavir	Reyataz®	Protease inhibitor/HIV	
Bedaquiline	Sirturo®	Anti-infective/Drug resistant Tuberculosis	Black Box for QT
Chloral hydrate	Noctec®	Sedative/sedation/insomnia	
Clozapine	Clozaril®	Anti-psychotic /schizophrenia	
Dolasetron	Anzemet®	Anti-nausea/nausea, vomiting	
Dronedarone	Multaq®	Anti-arrhythmic/Atrial Fibrillation	
Eribulin	Halaven®	Anti-cancer/metastatic breast neoplasias	
Famotidine	Pepcid®	H2-receptor antagonist/ Peptic ulcer/ GERD	
Felbamate	Felbatrol®	Anti-convulsant/seizure	
Fingolimod	Gilenya®	Immunosuppressant/Multiple Sclerosis	
Foscarnet	Foscavir®	Anti-viral/HIV infection	
Fosphenytoin	Cerebyx®	Anti-convulsant/seizure	
Gatifloxacin	Tequin®	Antibiotic/bacterial infection	Oral/I.V. forms no longer available in U.S. and Canada, only ophthalmic
Gemifloxacin	Factive®	Antibiotic/bacterial infection	
Granisetron	Kytril®	Anti-nausea/nausea and vomiting	
lloperidone	Fanapt®	Antipsychotic, atypical/ Schizophrenia	
Indapamide	Lozol®	Diuretic/stimulate urine & salt loss	
Isradipine	Dynacirc®	Anti-hypertensive/high blood pressure	
Lapatinib	Tykerb®	Anti-cancer/breast cancer, metastatic	
Lapatinib	Tyverb®	Anti-cancer/breast cancer, metastatic	
Levofloxacin	Levaquin®	Antibiotic/bacterial infection	
Lithium	Lithobid®	Anti-mania/bipolar disorder	
Lithium	Eskalith®	Anti-mania/bipolar disorder	
Mirtazapine	Remeron	Anti-depressant	
Moexipril/HCTZ	Uniretic®	Anti-hypertensive/high blood pressure	
Nicardipine	Cardene®	Anti-hypertensive/high blood pressure	
Nilotinib	Tasigna®	Anti-cancer/Leukemia	
Octreotide	Sandostatin®	Endocrine/acromegaly, carcinoid diarrhea	
Ofloxacin	Floxin®	Antibiotic/bacterial infection	
Olanzapine	Zyprexa®	Antipsychotic, atypical/ Schizophrenia, bipolar	Combo c fluoxetine: Symbyax
Ondansetron	Zofran®	Anti-emetic/nausea and vomiting	
Oxytocin	Pitocin®	Oxytocic/Labor stimulation	
Paliperidone	Invega®	Antipsychotic, atypical/ Schizophrenia	
Perflutren lipid microspheres	Definity®	Imaging contrast agent/ Echocardiography	
Quetiapine	Seroquel®	Anti-psychotic/schizophrenia	
Ranolazine	Ranexa®	Anti-anginal/chronic angina	
Risperidone	Risperdal®	Anti-psychotic/schizophrenia	
Roxithromycin*	Rulide®	Antibiotic/bacterial infection	*Not available in U.S.
Sertindole	Serdolect®	Antipsychotic, atypical/ Anxiety, Schizophrenia	Not available in U.S.
Sertindole	Serlect®	Antipsychotic, atypical/ Anxiety, Schizophrenia	Not available in U.S.
Sunitinib	Sutent®	Anti-cancer/RCC, GIST	
Tacrolimus	Prograf®	Immunosuppressant/ Immune suppression	
Tamoxifen	Nolvadex®	Anti-cancer/breast cancer	
Telithromycin	Ketek®	Antibiotic/bacterial infection	
Tizanidine	Zanaflex®	Muscle relaxant	
Vardenafil	Levitra®	phosphodiesterase inhibitor/ vasodilator	
Venlafaxine	Effexor®	Anti-depressant/depression	
Voriconazole	VFend®	Anti-fungal/anti-fungal	
Ziprasidone	Geodon®	Anti-psychotic/schizophrenia	

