3.2 Rationale for Study Design and Dose Levels

CAH is a rare disease with a limited number of potential subjects. Therefore, the study design must derive as much information as possible from each subject while simultaneously presenting as little risk as possible. This study protocol provides the potential for each subject to achieve the primary outcome measure at the lowest possible dose with a minimum duration of exposure (i.e. 14 days per dose level). In addition, the placebo Washout Period

ensures that each subject has returned to baseline status prior to receiving the next highest dose of ATR-101. This period also serves to verify that changes in adrenal steroids and steroid intermediates are due to ATR-101 effects. Thus, this protocol design will generate a robust dataset with a limited number of subjects which can establish proof of concept for the use of ATR-101 in CAH.

The starting dose for all subjects will be ATR-101 125 mg taken BID orally with food. This dose corresponds to approximately 3 mg/kg/day for a 75 kg individual and is intended to be a non-effective dose. While the 3 mg/kg/day dose was efficacious in dog studies, the exposures (i.e. $AUC_{0-24 \text{ hr}}$ mean $\sim 4700 \text{ ng}\cdot\text{hr}/\text{mL}$) were much higher relative to the projected corresponding exposures in humans. Based on pharmacokinetic modeling from the available human data (ACC subjects and healthy volunteer food effect study¹³), the 125 mg BID dose will provide a steady-state $AUC_{0-24 \text{ hr}}$ of $\sim 2308 \text{ ng}\cdot\text{hr}/\text{mL}$. Dose Level 2 (250 mg BID) will provide an $AUC_{0-24 \text{ hr}}$ of $\sim 4616 \text{ ng}\cdot\text{hr}/\text{mL}$. Each subsequent dose level (3, 4 and 5) will increase the ATR-101 dose by 500 mg per day, with projected steady-state $AUC_{0-24 \text{ hr}}$ values of ~ 9234 , 13850 and $18467 \text{ ng}\cdot\text{hr}/\text{mL}$, respectively. Thus, the projected exposures span a non-effective range up to approximately 4-times the effective exposure observed in the dog studies which allows for potential pharmacokinetic/pharmacodynamic differences between dogs and humans.

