4.3 Exclusion Criteria

Subjects who meet any of the following criteria will be excluded from participation in the study:

1. Non-classic CAH
2. Other causes of adrenal insufficiency such as Addison's disease; adrenalectomy etc.
3. Surgery within the previous three months prior to screening or planned surgery during study participation. Minor procedures are permitted (e.g. removal of skin tags or other minor dermatological procedures)
4. Abnormal laboratory tests at Screening:
 - ALT or AST >2 x ULN
 - Bilirubin >1.5 x ULN
 - Serum Creatinine >1.5 x ULN
5. History of active cancer requiring medical or surgical therapy within the past 6 months (with the exception of successfully treated non-metastatic basal cell or squamous cell carcinoma of the skin and carcinoma in-situ of the cervix)
6. Significant comorbid medical condition(s) that may preclude compliance with the study protocol or such that study participation may not be in the subject's best medical interest. Medical conditions may include (but are not limited to) those of the cardiovascular, respiratory, gastrointestinal, renal, hepatic, central nervous system (CNS) or immune system [(e.g., human immunodeficiency virus (HIV)], Myocardial infarction (MI) or cerebrovascular accident/transient ischemic attack (CVA/TIA) within the past 6 months
7. An average QTc value (Fridericia correction) of > 470 msec at Screening
8. Psychiatric illness such that comprehension of the informed consent or compliance with the study protocol may be impaired
9. Positive screen for HIV, Hepatitis B surface antigen or Hepatitis C antibody at Screening
10. Pregnant or lactating females
11. Current or ongoing use of any prohibited concomitant medications (Section 5.3)
12. History of substance abuse within the past 2 years prior to informed consent
13. Positive toxicology screening test for substances of abuse
14. Known allergy to ATR-101
15. Treatment with another investigational drug or device within 3 months prior to Screening

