5.3.1 Timing and Administrative Dosing Conditions

IMP should be taken approximately 12 hours apart (twice per day dosing). The time of day that the dose is taken should be as consistent as possible (e.g. every morning at 8AM and every evening at 8PM).

IMP should be taken immediately after consumption of food. No specific food contents are required and subjects should maintain usual eating practices. If a full meal is not possible or not aligned with a subject's usual eating practices, a light snack should be consumed prior to taking IMP.

The first dose of each bottle will be administered at the site prior to PK sampling. Subjects will be provided with food to consume prior to dose administration. See Pharmacy Manual for more details.

Grapefruit, grapefruit juice and other foods containing grapefruit should be avoided to prohibit possible interactions in the metabolism of ATR-101 or other concomitant medications.

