5.3.10 Prohibited Medications

ATR-101 is metabolized by several cytochrome P450 enzymes (CYPs) including CYP3A4. Concurrent use of drugs known to be metabolized by this pathway should be avoided. (Appendix 4).

ATR-101 is most soluble in acidic conditions. Proton pump inhibitors are prohibited and calcium preparations and antacids should not be used 2 hours before to 2 hours after ATR-101 administration.

Grapefruit and grapefruit juice are known to inhibit CYP3A4. Grapefruit products should be avoided.

Concurrent use of medications that are known to prolong the QT/QTc interval at therapeutic exposures are not permitted while on this protocol (Appendix 3, List A). Drugs that only cause prolonged QT intervals in unusual circumstances (e.g., overdose) may be used with caution (Appendix 3, Lists B and C).

Preclinical data indicate that ATR-101 may compete with certain drugs for P-glycoprotein in the intestinal lumen. The drugs listed in Appendix 5 should be used with caution, as they may have an impact on the level of ATR-101 or vice versa. Note that some of these drugs may also appear in Appendices 3 or 4, and may be contraindicated by those properties.

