5.4 Restrictions, Precautions and Warnings

Preclinical studies have identified adrenal suppression with apoptotic histologic changes. Such changes were associated with exposure levels much higher than what is anticipated for this study. However, occurrence of such changes is a possibility. The investigative staff should be familiar with the warnings and precautions for ATR-101 as presented in the Investigator's Brochure.¹⁰

ATR-101 is metabolized by CYP enzymes and is an inhibitor and inducer of CYP enzymes, and as a consequence, ATR-101 may interfere with the metabolism of other medicines also metabolized by CYP, especially CYP3A4. The metabolism of ATR-101 may be affected by other medicines or foods such as grapefruit products that inhibit CYP3A4. Such medicines and grapefruit products must be avoided. ATR-101 is an inhibitor of P-gp and OATP1B1.

Glucocorticoids are CYP substrates so there is the potential for increased GC levels. Glucocorticoid levels will be measured during the course of the study.

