6.9 Pharmacokinetic Assessments

Blood samples will be collected to profile the levels of ATR-101 and its metabolites at multiple days and times throughout the study. Assessment of ATR-101 levels may help to determine or establish pharmacokinetic and pharmacodynamic relationships. ATR-101 exposure levels may also help in the assessment of safety events. Sampling time points are presented for each of the applicable study days in Table 4. Samples for PK analysis will be taken prior to the first dose of ATR-101 (for each dose level) and up to 4 hours, post-dose. This time period is designed to capture the C_{max} (T_{max} is approximately 2 hours) and a few additional time points. Following the completion of the 14 day ATR-101 dosing period a single PK sample will be collected to assess trough levels of ATR-101 (morning of day 15). Subjects will then enter the 14 day placebo Washout Period. After completion of the placebo Washout period, subjects will either proceed to the next Dose Level and perform the same PK sampling as Day 1, or subjects will complete the Final Study Visit and do the same PK sampling as Day 15.

PK results will not be used to determine dose escalation. Approximately 4 mL of blood will be drawn at each sampling time point.

Table 4 Pharmacokinetic Sampling Time Points.

Visit	Sampling Time Point
Dose Level N, Day 1	Pre-dose, post-dose at 1, 2, 3, and 4 hours
Dose Level N, Day 15	Pre-dose, single blood draw

N=Dose Levels 1-5

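### Section 5.3.10 restricts acid-reducing drugs because ATR-101 dissolves best in acid, but sets no rule for H2-receptor antagonists, so famotidine stays usable under a QT-only caution

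*Protocol*

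**What the plan says.** Protocol Section 5.3.10 gives both a reason and a rule: "ATR-101 is most soluble in acidic conditions. Proton pump inhibitors are prohibited and calcium preparations and antacids should not be used" within two hours either side of an ATR-101 dose. H2-receptor antagonists are not mentioned.

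The same section deals with QT-prolonging drugs separately. Those on List A are not permitted, while the drugs on the other two lists "may be used with caution (Appendix 3, Lists B and C"). Famotidine is on List C, with its class and use given as "H2-receptor antagonist/ Peptic ulcer/ GERD" and nothing in the Comments column. It is in neither Appendix 4 (CYP3A4) nor Appendix 5 (P-glycoprotein).

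Cimetidine, another H2-receptor antagonist, is listed in Appendix 4 as a CYP3A4 inhibitor. Section 5.4 says of CYP3A4 inhibitors: "Such medicines and grapefruit products must be avoided". So one member of the class is caught, for a reason unrelated to acid.

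Exclusion 11 in Section 4.3 reads "Current or ongoing use of any prohibited concomitant medications (Section 5.3"), so it reaches only what Section 5.3 prohibits.

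**The concern.** The protocol's own reason for restricting proton pump inhibitors and antacids extends to any drug that lowers stomach acid. A site that looks up famotidine finds a permission with a QT caution and nothing about absorption. A subject could therefore take it throughout a 14-day ATR-101 treatment period without breaching a listed restriction. Such use would not clearly trigger exclusion 11, a deviation from the medication restrictions (Protocol 10.8), or replacement for prohibited medication (Protocol 9.1).

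If acid suppression reduces absorption, that subject's exposure is below what the dose level is meant to deliver. The Day 15 17-OHP response could be weaker, or could come only at a higher level. PK/PD plots would gain noise. Low exposure would not be corrected during the study, because Protocol 6.9 states: "PK results will not be used to determine dose escalation".

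**Working it through.** **What covers each acid-reducing drug**

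| Drug or class | Rule | Ground |
|---|---|---|
| Proton pump inhibitors | Prohibited (5.3.10) | Acid |
| Calcium preparations, antacids | Two-hour separation (5.3.10) | Acid |
| Cimetidine | To be avoided (5.4, Appendix 4) | CYP3A4 |
| Famotidine | Caution only (5.3.10, List C) | QT |
| H2-receptor antagonists in no list | None | None |

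**Inputs.** Protocol 3.2 projects steady-state AUC0-24 (ng·hr/mL) at 2,308, 4,616, 9,234, 13,850 and 18,467 for Levels 1 to 5, and says: "Each subsequent dose level (3, 4 and 5) will increase the ATR-101 dose by 500 mg per day". The documents give no effect of any H2-receptor antagonist on ATR-101 exposure and no frequency of use. The losses r below are assumptions.

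**Reproducing the plan's projections.** Dose-proportional scaling is 2,308 × daily dose / 250. It matches the stated values to within 0.03%.

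| Level | mg/day | Plan | Scaled | r = 10% | r = 25% | r = 50% |
|---|---|---|---|---|---|---|
| 1 | 250 | 2,308 | 2,308 | 2,077 | 1,731 | 1,154 |
| 2 | 500 | 4,616 | 4,616 | 4,154 | 3,462 | 2,308 |
| 3 | 1,000 | 9,234 | 9,232 | 8,311 | 6,926 | 4,617 |
| 4 | 1,500 | 13,850 | 13,848 | 12,465 | 10,388 | 6,925 |
| 5 | 2,000 | 18,467 | 18,464 | 16,620 | 13,850 | 9,234 |

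**User against non-user.** The loss that brings a user down to a non-user's exposure one level lower is 1 − (lower AUC / own AUC):
- Level 2: 1 − 2,308/4,616 = 50.0%
- Level 3: 1 − 4,616/9,234 = 50.0%
- Level 4: 1 − 9,234/13,850 = 33.3%
- Level 5: 1 − 13,850/18,467 = 25.0%

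A 10% loss reaches none of these thresholds. A 25% loss reaches only Level 5.

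**Within a continuous user.** A constant loss multiplies every level by (1 − r), which cancels in the ratio of one level to the next. At r = 50%, Level 4 over Level 3 is 6,925/4,617 = 1.5, the same as 13,850/9,234 = 1.5. Dose order within the subject is preserved.

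**Effect on a level's mean.** If n subjects have equal exposure A and one loses a fraction r, the mean is [(n − 1)A + (1 − r)A]/n = A(1 − r/n). This assumes that all n reach the level.
- n = 9: 0.25/9 = 2.8%; 0.50/9 = 5.6%
- n = 17: 0.25/17 = 1.5%; 0.50/17 = 2.9%

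The SAP also reports geometric means for Cmax and AUC. For one user among 9 the multiplier is (1 − r)^(1/9): 0.969 at 25% and 0.926 at 50%, falls of 3.1% and 7.4%.

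**Which PK results this touches.** SAP 6.10.1 and 6.10.4 take the by-level parameters from Day 1 samples, pre-dose to 4 hours. They move only if acid is suppressed at that dose. Famotidine started later in the period would leave the Day 1 parameters intact while possibly lowering the exposure behind the Day 15 17-OHP value, so the two would no longer correspond.

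**The case against.** The strongest case against is that the harm is inferred. The documents say where ATR-101 is most soluble but give no pH-solubility data, no interaction result and no expected famotidine use. Section 5.4 refers to the Investigator's Brochure and Section 5.3.1 to the Pharmacy Manual; either might address this. All of that stands, and it is why the sizes above are assumptions and the wording is conditional.

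Existing provisions also help. Protocol 5.3.1 says "IMP should be taken immediately after consumption of food". Section 5.3.8 tells sites to limit other treatment. SAP 6.6 summarizes concomitant medication by dose level and treatment, and Protocol 9.8 analyses individual PK, so an affected subject could be recognized afterwards. These limit the problem without closing the gap: the protocol requires food and limits other drugs, yet still restricts the other acid reducers. Recording use does not prevent it.

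It could be argued that antacids were meant to include famotidine. Section 5.3.10 names classes one by one, and List C gives famotidine a different class, so a site would not read it that way.

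A reader might infer that dose levels would collapse into one another or reverse, since 6,925 at Level 4 is below 9,234 at Level 3. The documents do not support that. The comparison sets a user against a non-user, and escalation here is within subject, where a constant loss keeps the order.

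**Conclusion.** The gap is real and the point is minor. Section 5.3.10 leaves one acid-reducing class outside a rule whose stated reason would cover it, and famotidine is the clear instance. The consequence falls mainly on the individual subject: possibly lower exposure, a weaker response or one delayed by 28 days per step, and noisier PK/PD. At an assumed 25% to 50% loss, a single user moves a level's mean exposure by 2.8% to 5.6% (n = 9) or 1.5% to 2.9% (n = 17). For the Day 1 parameters this applies only if acid is suppressed at that dose.

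Two stronger readings should be set aside. One is a safety concern from over-exposure: the mechanism puts true exposure below nominal, never above. The other is that the go/no-go decision is compromised: response may occur at any of five levels, and SAP 6.1 widens the Stage 1 criteria to count any mean percentage decrease in 17-OHP, so the effect there is likely small.

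**What to change.** In Protocol 5.3.10, add one sentence prohibiting H2-receptor antagonists, including famotidine, during ATR-101 treatment periods, as for proton pump inhibitors. If the sponsor's solubility data support a separation from dosing instead, state the interval. At famotidine in Appendix 3 List C, add a cross-reference to 5.3.10 so that the QT caution is not read as permission. Exclusion 11 then applies to a prohibited drug without rewording.

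No SAP change is needed. Any acid-reducing drug use can be noted when individual PK is interpreted, from medication data already collected.

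The cost is a sentence and a cross-reference. A few subjects may need another reflux treatment, such as spaced antacids, or be ineligible.
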